One benefit of gaining knowledge from this proposed study is to present valid and reliable data from these subjects with HFpEF in abstracts and full-length publications so that healthcare practitioners will have a better understanding of the effectiveness of oral ubiquinol, D-ribose, or both in treating patients with HFpEF. This would potentially change the clinical practice of cardiologists and healthcare practitioners in managing HFpEF and have a significant impact on implementing new changes in clinical guidelines for HFpEF.

5. Racial/Ethnic Data for Kansans.

Wyandotte County, Kansas - where the University of Kansas Medical Center is located - is profiled as multi-cultural, urban-centered, and medically underserved. The 163,369 residents make it one of the most densely populated counties in Kansas (1,039 persons per square mile). Females comprise 50.4% of the population in the county. Culturally, over 24.3% of the population is Black/AA; 27.8% Hispanic/Latino; 40.8% White; 1.3% Native American; 4.1% Asian; and 1.7% Alaskan Native, Native Hawaiian/Pacific Islander.⁹⁹ Kansas City, Kansas, is the largest city in the county; comprising 92.6% of the county population; 18.9% of residents (all ages) are Medicaid enrolled. The state of Kansas has 105 counties with a population of 2,911,641 with a racial/ethnic designation of 6.3% Black/AA, 11.6% Hispanic/Latino, 77.1% White, 1.2% American Indian, 2.9% Asian, and 0.9% Alaskan Native, Native Hawaiian/Pacific Islander. Out of 25,731 annual deaths (both sexes) in Kansas, 21.2% were due to heart disease. KU Hospital/KUMC is only 30 feet from the Kansas City, Missouri state line. The ethnicity of Kansas City, Missouri, includes: Black/AA 29.7%, Hispanic/Latino 10.1%, White 57.1%, American Indian 0.5%, Asian 2.4%, and 0.2% Alaskan Native, Native Hawaiian/Pacific Islander. KUMC receives referrals related to heart failure from both Kansas and Missouri. Data sources that document these data are: Kansas: Burden of Chronic Disease; CDC, 2012; Kansas Cancer Registry of The Kansas Department of Health and Environment (2000-2014); Kansas Department of Health & Environment, 2014; US Census Bureau (2015).

6. Recruitment Is from Sites Related to the PI's Community Involvement.

This includes the University of Kansas Hospital, Institute for Community Engagement and Frontiers: Heartland Institute of Clinical and Translational Research (HERON), Pioneers Community Registry, all of which have HF patients signed up to volunteer to participate in HF research. In addition, the Pioneers group has an agreement with Swope Health Services which is an inner city clinic that is over 60% Black/AA, 30% Hispanic/Latino, and 10% other races/ethnicity. Thus, we will screen at least 900 patients with HF across the 3-year study timeline. Of these 900 from various sources, we expect 600 patients will be eligible to enroll. Based on [name] recent HF trial, enrolling patients (N=276) from various registries and lists should be feasible.

7. We Proposed Several Research Plans to Overcome Any Problems.

Potential participants will be identified prospectively by the Mid-America Cardiology nurse study coordinator who reviews electronic medical records for 40 cardiologists. During recruitment, we will explain the various required time periods for testing and the different potential groups to which patients might be assigned. Our Project Director will assist us in recruiting subjects. Further, several previous study participants from [name] grant have volunteered to become involved in this study.

8. Investigators Involvement in Human Subjects Training.

The PI will assure that all members of the investigative team have completed and adhere to all requirements for the protection of human subjects. The PI will be involved in providing discussion and on-going education on the ethical conduct of research for the research team. The five NIH required instructional components (format, subject matter, faculty participation, duration, and frequency) are discussed herein. At each team quarterly meeting (duration and frequency) a standing agenda item will be core conduct of research topics. NIH recommends including conflict of interest, policies regarding human and animal subjects, research team members' responsibilities in collaborative research, peer review processes, quality data acquisition, and coding (subject matter). Samples of research misconduct and policies on responsible authorship and publication (subject matter) are reviewed. In the past meetings, formats of instruction have included report readings of NIH human subjects concerns, case study reviews, discussions regarding any current study issues arising from consultant input or collaborative work (format). We will invite our KUMC faculty leading the KUMC monthly ethics seminar/discussions to lead (faculty participation) some of these discussions on human and data safety and monitoring of scientific rigor and human safety. All staff members undertake the required human subjects research training, pledge to maintain the highest levels of scientific quality, and strive for meaningful translational influence of findings.

Data and Safety Monitoring Plan (DSMP).

The DSMP for this study follows the NIH policies and also policies of the University of Kansas Medical Center (KUMC) Office of Sponsored Projects, written by our Director of Research Compliance and Director of Research Administration. This plan will be approved and annually recertified by the Institutional Review Board (IRB) at the KUMC and carried out by an advisory group of reviewers that will be called the Data Safety

Monitoring Board (DSMB). This plan will be completed by the DSMB members, following review of the National Institute of Aging (NIA) Policy (if funded by this agency). The DSMB chairperson will send all reports to NIH and to our KUMC IRB.

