C.1. Study Population and Environment. The research protocol will first be approved by the Institutional Review Board, and all subjects will be provided with a written informed consent. The subject population, > 50 years of age, male and female with HFpEF, will be enrolled from the University of Kansas Medical Center (KUMC) Healthcare Enterprise Repository for Ontological Narration (HERON) database, Pioneers Recruitment Registry (Pioneers), and chronic HF clinic at the University of Kansas Hospital (KUH): 69 in the control (placebo) group; 69 in the ubiquinol group; 69 in the D-ribose group; and 69 in the ubiquinol plus D-ribose group, (total = 276). HERON provides clinical/translational investigators with the numbers of patients at KUH who meet the inclusion criteria for clinical trials and contact information for patients who sign up with KUMC's Frontiers participant registry. Based on the HERON, there will be approximately 7,100 subjects with HFpEF available to be screened for enrollment in this study. As suggested by the reviewers, we will oversample minority populations to increase the generalizability of data for minority groups (30% Black/African Americans (AA), 30% Hispanic/Latino, 30% White, and 10% American Indian/Alaska Native, Asian, Native Hawaiian/Pacific Islander). In addition, two nurse practitioners and a cardiologist on this application who work in the outpatient HF clinics will refer patients to the research team. All patients **included** in this study will: be 50 years old or older; have left ventricular ejection fraction (EF) \geq 50% documented by an echocardiogram within 12 months of enrollment; be diagnosed with HFpEF within a 12-month period; have symptoms of dyspnea and New York Heart Association (NYHA) Classification II or greater symptoms, have a diagnosis of HFpEF defined by one of the following: (1) previous hospitalization for HF with radiographic evidence (pulmonary venous hypertension, vascular congestion, interstitial edema, or pleural effusion) of pulmonary congestion, (2) invasive hemodynamics, (3) echocardiographic evidence of diastolic dysfunction, (4) elevated NT-pro (>400 pg/ml) or BNP (>200 pg/ml), or (5) no use of intermittent sublingual nitroglycerin within 12 months; have willingness to provide informed consent; have a telephone or reliable phone contact; and have their own means of transportation to the study site. Patients will be **excluded** based on any of the following criteria: (1) acute coronary syndrome in the past 12 weeks; (2) significant valvular heart disease; (3) severe cardiac fibrosis (galectin-3 level > 26 ng/ml); (4) constrictive pericardium; (5) pulmonary fibrosis; (6) congenital heart disease; (7) hypertrophic or infiltrative cardiomyopathy; (8) heart transplant; (9) left ventricular assist device; (10) HF associated hospital admission or emergency room visit within past 30 days; (11) recent percutaneous coronary intervention; (12) significant renal and/or hepatic dysfunction; (13) severe cognitive impairment; or (14) consumption of any CoQ10 (ubiquinol) or D-ribose supplements. Hepatic and renal dysfunction will be defined as an ICD-10 code with diagnosis of renal and/or hepatic failure in the patient's healthcare record. For retention we will schedule the sessions at a convenient time for each participant. Part of the recruitment plan includes subjects' preferences for conducting telephone calls and collecting data. All subjects will be asked to

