Initially, potential subjects from HERON, Pioneers, and KUH outpatient HF clinics will be interviewed by phone for potential recruitment in the study. Two nurse practitioners and a cardiologist on our research team work in the outpatient HF clinics and will refer patients to us. Patients will be required to speak English, and the informed consent and patient information will be written at the 8th grade level. We will collaborate with our Human Subject Protection Program to ensure our consent form complies with the US Department of Health and Human Services (HHS) federal guidelines and obtain informed consent from eligible patients (Appendix 10). Patients that have consented will be provided a 1-week supply of placebo ubiquinol pills (instructed to take 2 pills/day) and placebo D-ribose powder (instructed to take 3 scoops/day) as a pre-randomization run-in period to evaluate compliance to the supplements. Patients will be scheduled for an appointment at the CTSU in 1 week following the run-in period. Patients that demonstrate an 80% compliance rate of ubiquinol intake (as evidenced by pill count) and an 80% compliance rate of D-ribose powder intake (as evidenced by weight of the containers) will be eligible to be randomized into a group assignment. The enrolled patients with 80% compliance will then be randomized into four groups (69 subjects in each group) to receive ubiquinol (600 mg daily), D-ribose (15 g daily), ubiquinol plus D-ribose, or placebo for a period lasting 12 weeks. Both the ubiquinol and the D-ribose supplements used in the study will have a certificate of analysis from the manufacturer (Appendix 9). The Project Director will receive the identified list of recruited subjects from the Principal Investigator (PI) and will randomly assign subjects to one of the groups using a list created by a computer-based random number generator. All supplements and the placebo will be indistinguishable in packaging and will be distributed by the Project Director independent of the PI so that the allocation of subjects to a treatment or placebo group will be concealed from both subjects and research personnel.

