echocardiography on patients with HFpEF have demonstrated more sensitive measurements of changes of LV structure than regular echocardiography. Speckle tracking consistently showed early diastolic strain rate, reduced peak strain, and fibrosis as evidenced by increased myocardial reflectivity, which parallels the degree of diastolic dysfunction.⁵⁰⁻⁵² In this study, a speckle tracking echocardiography technician will perform the echocardiograms during each visit (baseline and 12 weeks). Drs. [name] (an expert in speckle tracking research), [name], and [name] (cardiologists) will determine EF and the ratio of mitral peak velocity of early filling (E) to early diastolic mitral annular velocity (e') (E/e' ratio) (SV, EDV, EF) from the echocardiogram. Using speckle tracking software, we will measure myocardial deformation, rotation, torsion, strain, strain rate, and tissue velocity. Changes in the early apical diastolic untwisting rate (rotR) and negativity of time from apical peak diastolic untwist (trotR) to mitral valve opening (MVO) are two major variables that reflect diastolic function. Decreases in rotR and trotR are indications of diastolic dysfunction.⁵³ Speckle tracking analysis with two-dimensional imaging will be performed as previously described by Leitman et al. at high frame rate parasternal short-axis images at the level of the mitral valve to generate rotation and rotation rate data.⁴⁷ Frame-by-frame rotation and rotation rate will be exported in Excel, and the temporal data will be normalized to the percentage duration of systole and diastole separately as previously described by Nakai et al.⁵⁴ We anticipate that ubiquinol and/or D-ribose will change rotR, trotR, strain, strain rate, and tissue velocity.

Potential Problem and Alternative Solutions. One issue that might arise relates to scheduling the echocardiographic technician when the subject is available to come to the CTSU. A solution is to utilize an additional on-call echocardiographic technician should scheduling issues occur.

Hypothesis #4. Ubiquinol (600 mg daily), D-ribose (15 g daily), or a combination of the two will increase the distance that patients with HFpEF can walk in 6 minutes.

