B-type natriuretic peptides are a cardiac neurohormone secreted from the atria and ventricles in response to volume expansion. This natriuretic peptide system assists in regulating extracellular volume by inducing renal diuresis.⁵⁹ Serum levels of BNP increase in cardiac disease conditions associated with increased atrial and ventricular stretch and left ventricular diastolic filling pressures. Miller et al. found that BNP concentrations were increased in outpatients with HF and were directly correlated with the magnitude of HF.⁶⁰ In one study of 1,653 subjects, the BNP levels increased as left ventricular dysfunction increased.⁶¹ Ruskoaho found that in the outpatient setting serum BNP values had a sensitivity of 97% and a negative predictive value of 98%.⁶² Increased BNP concentrations with diastolic dysfunction have been strongly related to left ventricular hypertrophy.⁶³ HF recommendations were updated in 2010 to include natriuretic peptides (i.e., BNP) in the urgent-care setting when the clinical diagnosis of HF is uncertain.⁶⁴ In HF patients with EF > 40%, natriuretic

peptides were the strongest independent predictor of diastolic dysfunction.⁶⁵ At time of discharge, a BNP level of 400 pg/ml was 89% sensitive for events, and the negative predictive value was 96%.⁶⁶ Independent of other prognostic variables, BNP levels have been shown to predict mortality in patients with HF.⁶⁷

BNP concentration will be measured using a portable i-STAT handheld analyzer. A blood sample (20 µl) will be obtained from a finger stick after the subjects have completed the questionnaires at baseline and 12 weeks. We will measure BNP concentration at each visit. Prior to running the BNP test, the cartridge initiates a series of preset quality control diagnostics, from monitoring the quality of the sample to validating the reagent. The i-STAT can detect BNP levels ranging between 5 and 5000 pg/ml, with results available in 10 minutes.

Hypothesis #6. Ubiquinol (600 mg daily), D-ribose (15 g daily), or a combination of the two will decrease the lactate/ATP ratio in patients with HFpEF.

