1.1. Human Subjects Involvement, Characteristics, and Design. The involvement of human subjects in the work outlined in the Research Strategy includes two visits to the Clinical and Translational Scientific Unit (CTSU), obtaining echocardiograms and digital punctures (finger sticks), completing questionnaires, and receiving three follow-up phone calls by research staff. As suggested by the reviewers, we will oversample minority populations to increase the generalizability of data for minority groups (30% African American (AA), 30% Hispanic/Latino, 30% White, and 10% American Indian/Alaska Native, Asian, Native Hawaiian/Pacific Islander). All patients **included** in this study will: be 50 years old or older; have left ventricular ejection fraction (EF) $\geq 50\%$ documented by an echocardiogram within 12 months of enrollment; be diagnosed with HFpEF within a 12-month period; HFpEF, have symptoms of dyspnea and New York Heart Association (NYHA) Classification II or greater symptoms, have a diagnosis of HFpEF defined by one of the following: (1) previous hospitalization for HF with radiographic evidence (pulmonary venous hypertension, vascular congestion, interstitial edema, or pleural effusion) of pulmonary congestion, (2) invasive hemodynamics, (3) echocardiographic evidence of diastolic dysfunction, (4) elevated NT-pro (>400 pg/ml) or BNP (>200 pg/ml), or (5) no use of intermittent sublingual nitroglycerin within 12 months; be 50 years old or older; have left ventricular ejection fraction (EF) $\geq 50\%$ documented by an echocardiogram; are diagnosed with HFpEF within a 6-month period; have willingness to provide informed consent; have a telephone or reliable phone contact; and have their own means of transportation to the study site. Patients will be **excluded** based on any of the following criteria: (1) acute coronary syndrome in the past 12 weeks; (2) significant valvular heart disease; (3) severe cardiac fibrosis (galectin-3 level > 26 ng/ml); (4) constrictive pericardium; (5) pulmonary fibrosis; (6) congenital heart disease; (7) hypertrophic or infiltrative cardiomyopathy; (8) heart transplant; (9) left ventricular assist device; (10) HF associated hospital admission or emergency room visit within past 30 days; (11) recent percutaneous coronary intervention; (12) significant renal and/or hepatic dysfunction; (13) severe cognitive impairment; or (14) consumption of any CoQ10 (ubiquinol) or D-ribose supplements. Hepatic and renal dysfunction will be defined as an ICD-10 code with diagnosis of renal and/or hepatic failure in the patient's healthcare record. For retention we will schedule the sessions at a convenient time for each participant. Two nurse practitioners and a cardiologist on this application who work in the outpatient HF clinics will refer patients to the research team. Also, potential patients with HFpEF who are in the Frontiers participant registry will be contacted, screened, and enrolled in the study. In this randomized, double-blind, placebo-controlled trial, eligible subjects will be randomized to receive either ubiquinol (600 mg daily po), D-ribose (15 g daily po), a

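### As written, not using sublingual nitroglycerin satisfies the list that defines HFpEF on its own, and the two eligibility sections disagree on the diagnosis window (12 months against 12 and 6).

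*Combined protocol and SAP*

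**What the plan says.** C.1 (Study Population and Environment) requires that patients "have a diagnosis of HFpEF defined by one of the following". Five numbered items follow, joined by an or:

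- (1) a past heart-failure admission with radiographic congestion;
- (2) invasive hemodynamics;
- (3) diastolic dysfunction on echocardiogram;
- (4) a natriuretic peptide above a stated limit;
- the last, "or (5) no use of intermittent sublingual nitroglycerin within 12 months".

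Section 1.1 of Participation of Human Subjects repeats the list with the same numbering, the same or and the same fifth item.

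On timing of the diagnosis, C.1 has one clause: "be diagnosed with HFpEF within a 12-month period". Section 1.1 has that clause too. After the list it then restates several criteria ("nitroglycerin within 12 months; be 50 years old or older; have left ventricular ejection fraction (EF" and onward), ending with patients who "are diagnosed with HFpEF within a 6-month period".

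C.2 adds a run-in. Patients who reach 80% compliance with both placebo products "will be eligible to be randomized into a group assignment". C.3 says that a technician "will perform the echocardiograms during each visit (baseline and 12 weeks") and, for BNP, "We will measure BNP concentration at each visit".

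**The concern.** The list is the only place where the protocol says what evidence must support the diagnosis. Items (1), (3) and (4) state positive findings. Item (5) states only that a drug was not used, so for anyone not using that drug the list asks for nothing more. It reads as a separate criterion that slipped into the list.

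The statistical stake is dilution. The supplements are expected to act on diastolic stiffness (A.4 and C.3). If some patients admitted through item (5) alone lack that disorder and respond less, the mean KCCQ difference shrinks toward zero and power falls. Randomization, blinding and type I error are not affected.

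The diagnosis window is a separate matter. Two sections that give different rules can lead to different decisions on the same patient. This has no bearing on the dilution argument.

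**Working it through.** **List logic.** Take a patient with items (1) to (4) all absent and no sublingual nitroglycerin in 12 months. One of five is required and item (5) is true, so the list is met. Next, ask whether anything else brings back a need for (1) to (4):

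- Recorded HFpEF diagnosis, EF of at least 50%, dyspnea, NYHA class II or greater: all still required, but none calls for any of (1) to (4).
- The 14 exclusions: they remove other conditions and do not confirm HFpEF.
- Run-in (C.2): compliance is added to the C.1 criteria and brings no diagnostic check.
- Baseline echocardiogram and BNP: taken in everyone, so these patients could be partly described afterwards, but neither result is a condition of randomization.
- C.5: no analysis is restricted to patients with (1) to (4). Apart from change scores, baseline E/e' appears only as a covariate in the mediation models.

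**Diagnosis window.**

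| Section | Window(s) stated |
|---|---|
| C.1 | 12 months |
| Section 1.1, before the list | 12 months |
| Section 1.1, after the list | 6 months |

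The criteria are cumulative. Reading both windows as time before enrollment, a patient diagnosed 6 to 12 months earlier passes C.1 and fails the last clause of section 1.1. The repeated age and EF cut-offs agree with the first statement; the EF repeat only drops the 12-month limit on the echocardiogram.

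**Illustration of dilution.** Inputs from C.5 are a 10-point KCCQ target, SD 12.3, 62 per arm, and two-sided alpha 0.05/4 = 0.0125. Noncentral-t power uses df = 122, critical value 2.535 and noncentrality (m/SD) × √(62/2).

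Plan's own figure first: (10/12.3) × √31 = 4.53, power 97.6% (97.9% by normal approximation). The plan states at least 98%, so it reproduces to within rounding.

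Now let f be the share entering on item (5) alone and r the fraction of the effect they gain. Both are assumed. The mean difference is m = 10 × (1 − f(1 − r)). With mixture variance, the active arm has v = 12.3² + f(1 − f)(10(1 − r))², and the pooled SD is √((12.3² + v)/2).

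| r | f | m | Power, SD 12.3 | Power, mixture variance |
|---|---|---|---|---|
| 0.5 | 10% | 9.5 | 96.0% | 95.8% |
| 0.5 | 20% | 9.0 | 93.6% | 93.3% |
| 0.5 | 30% | 8.5 | 90.3% | 89.8% |
| 0 | 10% | 9.0 | 93.6% | 92.9% |
| 0 | 20% | 8.0 | 85.9% | 83.8% |
| 0 | 30% | 7.0 | 73.6% | 70.1% |

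For BNP at the pilot effect size of 1.5, the worst cell (f = 30%, r = 0) gives 1.5 × 0.7 = 1.05 and 99.95% with fixed SD. With mixture variance, v = 1 + 0.21 × 1.5² = 1.4725, the pooled SD is √((1 + 1.4725)/2) = 1.112, the effect is 1.05/1.112 = 0.944, and power is 99.6%.

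**The case against.** The strongest reply is that the harm is hypothetical. Every entrant needs a recorded HFpEF diagnosis, preserved EF and symptoms, and must clear the exclusions. Many will come from heart-failure clinics, referred by a cardiologist or nurse practitioners. Nothing suggests that many such patients lack all of (1) to (4). This stands. It limits the likely effect but does not repair the rule.

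The contrast between the items can also be overdrawn. Item (2) names invasive hemodynamics without a result, so read literally it too states no finding. Only item (3) requires diastolic dysfunction; (1) and (4) show congestion or a raised peptide. This stands as well. Resting the definition on (1) to (4) does not guarantee that every entrant has the disorder that the supplements target.

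On the windows, C.1 does not say what the 12 months are counted from, and section 1.1 contains a stray fragment that suggests leftover editing. Both are fair, but the text still carries two different values.

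A reader might go further and infer that the sponsor accepts the absence of nitroglycerin as proof of HFpEF, or that the trial will enroll many patients without the disease and be underpowered. The documents support neither. Nothing shows intent, and neither the share nor the response is given. Nor should a reader infer that the biological outcomes are immune: BNP power is very high only at the pilot effect size, while C.5 also plans for effects of 0.7, where it claims at least 90% power (91.1% by the same formula) and so has less to spare.

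**Conclusion.** The concern holds as a defect in two eligibility rules as written.

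On the list, the text is unambiguous and the same in both sections: item (5) alone satisfies it, and nothing elsewhere restores a need for (1) to (4). The consequence is unknown in size. Over the assumed range the KCCQ loss is modest unless the share is large and the response near zero: with fixed SD, power drops below 90% only when these patients gain nothing and make up 20% or more of entrants. These figures rest on assumed shares and responses and on the plan's own 10-point effect and SD of 12.3. They are not a forecast.

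On the diagnosis window, section 1.1 contradicts both C.1 and itself. This is minor and a matter of consistency only.

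Both should be corrected. The certainty attaches to the wording, not to the size of any effect on the results.

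**What to change.** - In C.1 and in section 1.1 of Participation of Human Subjects, take item (5) out of the list so that the definition rests on items (1) to (4). The sponsor should state whether item (5) stands as a separate criterion.
- Reconcile the diagnosis window to one value, chosen by the sponsor and identical in both sections.
- Delete the repeated age and EF clauses in section 1.1.

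The cost is wording in two sections and some additional screen failures, whose number cannot be estimated from the documents. There appears to be some room: section 6 of Participation of Human Subjects expects 600 eligible patients for 276 places, although it does not say how item (5) was applied in reaching that number. Every entrant already needs an echocardiogram from the past 12 months, so item (3) may often be checked from that record, though the documents do not say that it includes diastolic measures.
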